**Mindfulness-Augmented Cognitive Behavioral Therapy for
Insomnia as a Phase 3 Treatment for Non-remittent Insomniacs
- An Open-label Pilot Study**

NCT03724305

March 8th 2023

1. Statistical Analysis Plan

Study outcomes were downloaded directly from Qualtrics and all analyses were performed in SPSS 241 version 26 (IBM Corp) with a significance value of .05. We first examined descriptive data for sample 242 characteristics, including sociodemographics, insomnia treatment history, and presenting clinical symptoms. 243 Study hypotheses were tested using a complete case analysis approach, which included all patients enrolled in 244 MBTI. As the study was a single-arm proof-of-concept clinical trial, we conducted paired samples t-tests to test 245 acute pretreatment to posttreatment effects of MBTI on mindfulness, sleep symptoms, depression, and cognitive 246 arousal. To test long-term effects, we conducted paired samples t-tests comparing study outcomes at 247 pretreatment and 6-month follow-up. Paired samples t-test effect sizes are expressed using Cohen's dz; 248 small=.20, medium=.50, large=.80, very large ≥ 1.00 . In addition, we conducted posthoc analyses to further 249 explore our data, which included examining frequency of Rx and OTC sleep aid use at posttreatment and 250 follow-up (note: reducing sleep aid use can be a goal of insomnia therapy, but this was not the case in the 251 present study; rather we observed spontaneous changes in sleep aid use), as well as rates of insomnia remission 252 and major depression among patients with high vs low cognitive arousal at posttreatment and follow-up.

2. Protocol

1. **STUDY AIM, BACKGROUND, AND DESIGN ABSTRACT**

Millions of people with untreated insomnia suffer from impaired daytime functioning, depression, and poor quality of life. Cognitive-behavioral therapy for insomnia (CBT-I) is a specialist-driven multicomponent treatment that is recommended as a first-line intervention with superior safety and durability relative to pharmacotherapy. Despite the demonstrated success of CBT-I, ~50% of patients do not achieve full remission.

Our research (NINR R01 and others) suggests that inadequate CBTI response is linked to residual symptoms of cognitive-emotional arousal (i.e., rumination, worry) ([name] et al., 2020; Kalmbach et al., 2019). Despite its role in insomnia etiology and maintenance, cognitive-emotional arousal is not a primary therapeutic target in standard CBTI, which has minimal effects on these symptoms. The link between residual cognitive-emotional arousal and treatment-resistance emphasizes a critical unmet need to address residual cognitive-emotional arousal symptoms in non-remittents. Though initial remission rates of 50-60% are good, this still leaves millions exposed to the harmful consequences of insomnia such as depression, daytime impairment, and decreased quality of life.

To address this critical limitation of CBTI, researchers have placed the behavioral sleep strategies of CBTI into a mindfulness intervention framework to create mindfulness-based therapy for insomnia (MBTI). Like CBTI, MBTI substantially reduces insomnia symptoms. Unlike CBTI, MBTI also substantially alleviates cognitive arousal (Ong et al., 2008; Ong et al., 2014). These data suggest that MBTI may be highly effective for treatment-resistant insomnia, which is marked by refractory cognitive arousal.

In this internally funded pilot study, we propose to test whether MBTI significantly reduces symptoms of insomnia and cognitive arousal in patients with highly treatment-resistant

insomnia. Forty patients who did not remit after at least one round of CBTI will be recruited from an ongoing stepped care trial (IRB # 11586) and will receive telemedicine MBTI in this open-label trial. Specifically, after patients in the stepped care trial do not fully remit after one (digital CBTI) or two (first-line digital CBTI followed by face-to-face in-person CBTI) rounds of treatment, we will invite them to participate in this trial in which all patients would receive telemedicine MBTI. We will assess insomnia, cognitive arousal, and other relevant symptoms before and after the 8 sessions of MBTI and then again 6 months following the end of treatment.

Aim 1: Determine whether MBTI reduces insomnia symptoms in highly treatment-resistant insomnia. We predict that patients will report a significant decrease in insomnia symptoms from pre-MBTI to post-MBTI.

Aim 2: Determine if MBTI reduces cognitive arousal in highly treatment-resistant insomnia. We predict that patients will report a significant decrease in cognitive arousal symptoms from pre-MBTI to post-MBTI.

These findings would be important as they would support the hypothesis that sleep can be improved in a highly resistant population of insomnia patients and that this improvement may be due to a decrease in cognitive emotional arousal. These findings would also allow clinicians to triage patients into more helpful therapies that better fit their cognitive emotional profiles and improve sleep and emotional well-being more quickly by targeting specific sleep issues.

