8. Six months after completion of the treatment sessions, a 6-month follow-up questionnaire (Drake_MBTI-STRIDE_Questionnaires) will be sent to the participant to complete.

Additional Information

- Assessments will occur at baseline, at completion of the 8-week intervention, and 6 months following completion of the intervention.
- Data will be collected using questionnaires on the Qualtrics survey platform for the following assessments at Pre-Treatment, Acute Post Treatment and then 6-Month

Follow-up time points

- Insomnia Severity Index (ISI)
- PHQ9
- Five-Facet Mindfulness Questionnaire – a measure of mindfulness insight
- Pre-Sleep Arousal Scale (PSAS) – a measure of nocturnal cognitive arousal
- PSWQ – a measure of cognitive arousal
- RRS Brood – a measure of cognitive arousal
- Perseverative Thinking Questionnaire (PTQ) – a measure of repetitive negative thinking
- Epworth Sleepiness Scale (ESS)
- Daytime Insomnia Symptom Response scale (DISRS)
- COVID-19 Questions
- Data analysis plan:
 - Power Analysis: Although MBTI produces large reductions in insomnia symptoms in prior trials (Cohen's $d > .80$), patients in this study are treatment resistant. Therefore, we anticipate that MBTI may have a reduced effect on insomnia symptoms. Based on a medium anticipated effect (Cohen's $d = .50$) for a two-tailed test with alpha = .05, a N = 34 sample size will have a .81 power to detect significant effects using within samples t-tests. To account for potential subject attrition, we thus request to recruit a sample size of 40 participants. Notably, in many of our prior insomnia therapy trials, attrition rates were <5%, therefore we are confident that a N=40 sample size will provide sufficient power to detect symptom changes in our primary and secondary outcomes
 - AIM 1: We will use an intent-to-treat approach using the last observation carried forward, which is a conservative method to address missing data/attritors in clinical trials. We will test changes in insomnia symptoms using paired-samples t-tests from pre to post MBTI. We will use a two-tailed test with significance set at alpha=0.05. Cohen's d will be used to describe effect size.
 - AIM 2: Analyses for Aim 2 will be the same as those for Aim 1, except we will examine changes in cognitive arousal.
 - The team member performing the statistical analysis will be provided with de-identified demographic data and questionnaire answers.
- Therapy Content

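### The 6-month test drops patients without a 6-month score and ignores their posttreatment scores, so it overstates the long-term effect if poor responders are less likely to return

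*Combined protocol and SAP*

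**What the plan says.** The SAP (section 1, Statistical Analysis Plan) defines the analysis set in one sentence: "Study hypotheses were tested using a complete case analysis approach, which included all patients enrolled in" MBTI. For the later time point it says: "To test long-term effects, we conducted paired samples t-tests comparing study outcomes at" pretreatment and 6-month follow-up. Effect sizes are Cohen's dz.

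The protocol (section 3, Additional Information) collects the same questionnaires three times: "Assessments will occur at baseline, at completion of the 8-week intervention, and 6 months following completion of the intervention". Its data analysis plan has a different missing-data rule: "We will use an intent-to-treat approach using the last observation carried forward, which is a conservative method to address missing data/attritors in clinical trials". That rule stands under Aim 1, is extended to Aim 2, and is tied to one contrast: "We will test changes in insomnia symptoms using paired-samples t-tests from pre to post MBTI". Neither document gives a missing-data rule, an expected loss or a sensitivity analysis for 6 months.

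Three other protocol sections bear on loss. Section 4 provides for removing participants who show significant distress. Section 6 says there is no payment. Section 10 allows data collected before withdrawal to be kept for analysis.

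**The concern.** A paired t-test of pretreatment against 6 months needs both scores and uses nothing else. A patient who completed the posttreatment questionnaire and then did not answer at 6 months contributes nothing, although the posttreatment score is the best available guide to the missing one.

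This matters when return is related to response. The 6-month assessment is an emailed questionnaire, unpaid, half a year after the last session. If patients who did poorly at posttreatment answer less often, the remaining patients are a favourable subset and the mean change looks better than it was. With no control arm, nothing offsets this. The result at stake is the claim that the benefit lasts.

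The analysis set is also unclear. A complete-case set equals all enrolled patients only if nobody is missing, and neither description matches the protocol's rule.

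**Working it through.** **The plan's own figure.** The protocol gives power .81 for N = 34 and d = .50, "for a two-tailed test with alpha = .05". The exact noncentral t (df = 33, noncentrality .50 × √34 = 2.92) gives .808, so the figure reproduces. Recruiting 40 to keep 34 allows for 6/40 = 15% loss. The protocol also says attrition was below 5% in many of the team's prior trials, without saying whether that covers 6-month follow-up. So 5% and 15% are anchored in the protocol; 25% is an assumption.

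**Assumed inputs (not in the documents).** Correlations: .40 pre-post, .35 pre-6-month, .70 post-6-month. True pre-to-6-month change: -.40 baseline SD. The log-odds of not returning rise by b = 1 to 1.5 per SD of worse posttreatment score. SDs at pre/post/6-month are 1/1/1 or 1/1.2/1.2.

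**Formula.** Let m be the mean standardised posttreatment score among those who return (negative, because higher scores are worse). Then

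bias = [Cov(post, 6-month − pre) / SD(post)] × m.

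- SDs 1/1/1: (.70 − .40) / 1 = .30.
- SDs 1/1.2/1.2: (.70 × 1.2 × 1.2 − .40 × 1 × 1.2) / 1.2 = (1.008 − .480) / 1.2 = .44.

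The bias is zero when loss is random (m = 0) or when the posttreatment score is uncorrelated with the pre-to-6-month change (covariance 0). Integrating the logistic return model numerically gives m:

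| Loss | b | m | Complete case, SDs 1/1/1 | Complete case, SDs 1/1.2/1.2 |
|---|---|---|---|---|
| 5% | 1 | -.047 | -.414 | -.421 |
| 5% | 1.5 | -.065 | -.419 | -.429 |
| 15% | 1 | -.133 | -.440 | -.458 |
| 15% | 1.5 | -.175 | -.453 | -.477 |
| 25% | 1 | -.213 | -.464 | -.494 |
| 25% | 1.5 | -.277 | -.483 | -.522 |

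For example, at 15% and b = 1: -.40 + .30 × (-.133) = -.440. If b applies per baseline SD instead, it becomes 1.2 times as steep in the last column, and the largest values become -.43, -.49 and -.53.

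Simulation at N = 40 (at least 20,000 trials per setting) reproduces these means. A likelihood estimate using all three time points stays within about .005 of -.40.

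**False positives.** With no true effect and SDs 1/1.2/1.2, two-sided rejection at .05 is about 5% at 5% loss, about 6% at 15% (up to 7% with the steeper slope) and 7% to 9% at 25%.

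**Second parameterisation.** This one is in SDs of the pre-to-6-month change, the scale of dz, with a correlation ρ of .3 to .7 between posttreatment change and 6-month change. Non-return depends on poor posttreatment change (slope 1 or 2 per SD; 8,000 trials per setting). Complete-case bias is +.01 to +.06 at 5% loss, +.04 to +.14 at 15% and +.08 to +.26 at 30%. At 15% and ρ = .5 it is +.07 to +.11, or 13% to 21% of the planned .50. In the extreme case where exactly the worst responders never return, bias = ρ φ(z_q)/(1 − q). At ρ = .7 that gives .7 × .103/.95 = .08, .7 × .233/.85 = .19 and .7 × .348/.70 = .35 at 5%, 15% and 30% loss.

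**Limits of the repairs.** If return depends on the unseen 6-month change, bias at 15% loss is +.13 to +.21 for complete cases and +.07 to +.19 for the likelihood estimate. Carrying the last observation forward is not a safe substitute. At 15% loss related to posttreatment response, with a stable true effect, it was biased by -.03 to -.12. Under random loss, with the effect falling from .5 to .3, it was biased by +.03.

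**The case against.** The strongest reply is that no bias has been shown. The SAP is in the past tense and says all enrolled patients were included. Taken literally, nobody was lost and the bias is zero. The only attrition experience quoted is below 5%, where the bias is .01 to .03 SD against a standard error of about .185 (change SD √(2 − 2 × .35) = 1.14, divided by √38). The aims and the planned tests in the protocol concern pre-to-post change only, and this is an uncontrolled proof-of-concept pilot.

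Much of this stands. A reader might infer that the reported 6-month effect is inflated. The documents do not support that: they give neither the number with 6-month data nor any evidence that return was related to response. The provision for removing distressed participants and the absence of payment make such loss plausible, no more.

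What does not stand is treating the all-enrolled statement as the answer. It sits in the same sentence as complete case and comes with no count, and the below-5% remark is not stated to cover 6 months. Nor does the limited role of the 6-month contrast remove the point, because the SAP itself presents it as the test of long-term effects.

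**Conclusion.** The point holds conditionally, as something the plan should change. The 6-month test discards posttreatment scores that are collected on the same instruments and may be kept after withdrawal. If poor posttreatment responders return less often, it overstates the effect. Under the assumptions above, that is by 3% to 8% at 5% loss, 10% to 21% at the protocol's own 15% allowance, and 16% to 34% at 25%. It is negligible at the attrition the protocol quotes and matters from about 15%. If loss is unrelated to the pre-to-6-month change, there is no overstatement. The correlations, SDs and dropout slopes are all assumed.

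The conflict between complete case, all enrolled patients and the protocol's carried-forward rule needs no assumption. That rule covers pre-to-post change only, so it does not fill the gap at 6 months. A reader might also infer that a mixed model would remove the bias; it does so only if return depends on observed scores.

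**What to change.** For each outcome, replace the separate complete-case t-tests with one repeated-measures mixed model: time as a three-level factor, unstructured covariance, REML, small-sample degrees of freedom, and every enrolled patient with any score. Take the pre-to-post and pre-to-6-month contrasts, with 95% confidence intervals, from that model. Keep the paired t-tests as a sensitivity analysis. Add a sensitivity analysis in which non-return depends on the unseen 6-month score, for example by shifting the imputed 6-month scores of non-returners by a range of amounts in the unfavourable direction. Report the number with data at each time point. State one analysis set and one missing-data rule per contrast, and explain any departure from the protocol's rule. If the count shows that nobody was lost, say so; the bias question then falls away.

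The cost is SAP wording, one SPSS MIXED run per outcome and the sensitivity runs; no new data are needed. The downside is that the model relies on data being missing at random given the observed scores. That is not simply a weaker assumption than the one complete-case analysis makes, and bias is reduced rather than removed if return depends on the unseen outcome.

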2. SUBJECT POPULATION AND ELIGIBILITY

Subject Population – Inclusion criteria

- Previous participation in both Phase 1 and/or Phase 2 of the STRIDE (Sleep to Reduce Incident Depression Effectively, IRB 11586) clinical trial will serve as the recruitment entry point for this pilot study. Insomnia patients (DSM-5) will have all received standardized digital CBTI (dCBTI) (Sleepio) (Phase1). Although most insomnia patients respond to dCBTI, only ~50% fully remit. dCBTI non-remitters (ISI >7) and participants who were then re-randomized to standard face-to-face CBTI (Phase 2), but were still non-remittent, will be offered mindfulness-augmented CBTI (MBTI) delivered by nurse via telemedicine real-time video (Phase 3).
- Patients who were non-remittent following face-to-face CBTI with a Behavioral Sleep Clinician are also eligible to participate in the study. These would be identified using chart-review.
- No vulnerable populations will be involved, although participants who are Henry Ford employees will be offered the chance to participate if they meet the study criteria (still non-remittent for insomnia after dCBTI and/or face-to-face CBTI therapy).
- English literacy
- Participants must have access to a device (cell phone, computer, or tablet) with audio and video capability.

Enrollment and/or Screening

- Participants will be identified by:
 - 2-year follow-up questionnaires from STRIDE (Sleep to Prevent Incident Depression Effectively, IRB 11586). Participants must have an ISI (Insomnia

Severity Index) > 7 at the 2-year follow-up to qualify for this pilot study.

- Chart-review from HFHS Epic records
- Prospective participants will be approached by email and phone (Drake_MBTI-STRIDE_Recruiting Materials). No additional screening other than what has previously been described is necessary.

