3. STUDY PROCEDURES

1. Potential participant is identified based on Insomnia Severity Index (ISI) score from STRIDE Timepoint 5 (2-year follow-up questionnaire), referral, or chart-review. ISI score greater than 7.
2. Prospective participant is contacted by email and/or phone and the additional study is described by the RN-Research Coordinator (RC) or Clinical Research Assistant (RA). Interested participants will be emailed the Informed Consent Form (ICF) in the form of a Qualtrics questionnaire. At the end of the Qualtrics questionnaire, the participant is given the option of a) Declining to participate, b) Agreeing to participate, or c) Expressing interest but would like more information. A video visit will be scheduled for the latter two options.
3. During the video visit, the RC or RA will review the ICF with the participant, explaining in detail the components of the study and answering all questions the participant has. If the participant would still like to move forward and participate, a second ICF Qualtrics questionnaire will be emailed with a signature page for the participant to sign and submit. A digital version of the HIPAA consent will also be discussed, and participants will be invited to sign. Participants will be able to have digitally signed copies of both documents for their records.
4. Once consent has been received, a baseline questionnaire (Drake_MBTI-STRIDE_Questionnaires) will be sent by email to the participant through the Qualtrics platform.
5. A tentative schedule for the 8 sessions will be determined and sent to the participant for reference. Schedules are flexible and can be changed by either the participant or the nurse therapist as required.
6. Eight sessions will be completed according to the Session Outlines (Drake_MBTI-STRIDE_Session Guide). Homework, consisting of a meditation log (Drake_MBTI-STRIDE_Participant Handouts) and a sleep diary (Drake_MBTI-STRIDE_MBTI Sleep Diary), are assigned to the participant each week for completion. Immediately prior to each session, a short Qualtrics questionnaire (Drake_MBTI-STRIDE_Treatment survey) will be emailed to the participant to complete; this questionnaire asks the participant questions about sleepiness, mood, and insomnia severity) to allow the clinician an opportunity to monitor the well-being of the participant each week.
7. At the conclusion of the eight sessions an end-of-study questionnaire (Drake_MBTI-STRIDE_Questionnaires) will be sent to the participant to complete.

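### Do the post hoc remission rates wrongly count patients whose ISI was already 7 or below before MBTI began?

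*Combined protocol and SAP*

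**What the plan says.** The remission rates appear once, in the last sentence of the Statistical Analysis Plan. That sentence opens with "In addition, we conducted posthoc analyses to further" and ends with "as well as rates of insomnia remission" and "major depression among patients with high vs low cognitive arousal at posttreatment and follow-up". It gives no ISI cutoff, no denominator and no condition on the pretreatment score.

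The cutoff has to be taken from the protocol. Section 2 (Subject Population and Eligibility) describes "dCBTI non-remitters (ISI >7", so remission is implied as an ISI of 7 or below. For the STRIDE route the same section requires "Severity Index) > 7 at the 2-year follow-up to qualify for this pilot study". Section 3 (Study Procedures), step 1, adds other routes: "Timepoint 5 (2-year follow-up questionnaire), referral, or chart-review. ISI score greater than 7". No maximum interval to the first session is given, and section 2 asks for no further screening. The pretreatment ISI is collected after consent (section 3, step 4 and Additional Information) with no threshold attached.

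The stated hypotheses are tested by paired t-tests from pretreatment to posttreatment, and to 6 months in the SAP.

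**The concern.** The score that admits a patient and the score from which treatment starts are taken on different occasions. ISI fluctuates, so some patients selected for an earlier value above 7 may be at 7 or below when MBTI begins. If they are still there afterwards, a rate over all patients counts them as remitted although they did not move from non-remission to remission during MBTI.

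The background section invites the reading that would make this matter. It uses remission as the result of a treatment: "50% of patients do not achieve full remission" for CBT-I, and "Though initial remission rates of 50-60% are good". A reader who set the MBTI rate beside that 50-60% would be comparing unlike quantities, and the MBTI figure would err upward. The split by arousal could suffer too. If arousal and ISI are correlated, patients who started low would gather in the low-arousal group and widen the contrast that the protocol's proposed mechanism predicts.

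**Working it through.** **1. What the sentence means.** Remission and major depression share one grouping (arousal) and one pair of time points (posttreatment and follow-up). A rate of major depression at posttreatment is a status: who meets the criterion then, out of everyone assessed. The parallel construction gives remission the same meaning. Section 2 of the protocol also classifies remission by where a single ISI lies relative to 7, with no element of change. For a status rate, leaving out patients who started at 7 or below would be the mistake.

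**2. What the plan does with it.** The only comparison described is higher against lower arousal within this sample. No section sets the MBTI rate against the 50-60% for CBTI. Change under MBTI is assessed by the paired t-tests, which use the pretreatment ISI. The one design figure, power .81 at N = 34, d = .50 and two-sided alpha .05, reproduces: with df = 33 and noncentrality 0.5 × √34 = 2.92 the exact power is 0.808. It does not involve the remission rates.

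**3. How far the two rates could differ.** Let k of N patients start at 7 or below, s be the share of them at 7 or below afterwards, and p the rate among the others.

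All-patient rate = [p(N − k) + s·k]/N, so the excess over p is (k/N)(s − p).

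If k = 0 the excess is zero. The documents give none of k, s or p, so every figure below is an assumption.

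**4. Model.** Normal ISI, rounded and held to 0-28; SD 5; pool mean 10-14; correlation .6-.8 between occasions; dz 0 to 0.5; N = 40. The arousal rows assume a median split with 20 per group and a correlation of .3-.5 with posttreatment ISI.

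| | Two earlier scores > 7 | One earlier score > 7 |
|---|---|---|
| Start at 7 or below | 3.2-13.5% (1.3-5.4 of 40) | 4.7-18.7% (1.9-7.5 of 40) |
| Excess of all-patient rate, points | 0.8-4.1 | 1.5-6.6 |
| Standard error of that rate, points | 2.8-7.1 | 3.4-7.5 |
| Excess in standard errors | 0.26-0.58 | 0.38-0.91 |
| Widening of arousal contrast, points | 0.7-3.1 | 1.3-5.1 |
| Standard error of contrast, points | 5.5-14.0 | 6.6-14.8 |
| Restricted rate with no treatment effect | 2.4-10.7% | 3.2-13.5% |

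Patients who went through both STRIDE phases can have three earlier scores above 7. The same model then gives 2.5-10.6% starting at 7 or below and an excess of 0.5-2.9 points.

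Central example (mean 12, r = .7, dz 0.5, two scores): k = 2.8, all-patient rate 16.3%, restricted rate 13.8%. The excess is 2.5 points against √(.163 × .837/40) = 5.8 points, or 0.43 standard errors. Remitted patients number 40 × .163 = 6.5 in all and 37.2 × .138 = 5.1 in the restricted group, so about 1.4 of the 2.8 are still low afterwards (s about .5).

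**5. Harsher assumptions.** With pool mean 8-12, SD 4-6, correlation .5-.8 and one earlier score, 6-31% start at 7 or below, about 2-12 of 40. Take p = 40% and let all of them stay low (s = 1):

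- k = 4: (.4 × 36 + 4)/40 = 46%; excess 6 points, standard error 7.9
- k = 8: (.4 × 32 + 8)/40 = 52%; excess 12 points, standard error 7.9
- k = 12: (.4 × 28 + 12)/40 = 58%; excess 18 points, standard error 7.8

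So the statement that the excess is below one standard error belongs to the model in step 4. It can be exceeded if many patients start low and all stay there.

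**6. What restriction would leave.** With no treatment effect, 2.4-13.5% of the restricted group would still cross the cutoff. Scenario by scenario in the step 4 model, that is 1.8 to 4.6 times the no-effect excess that restriction removes. The restricted rate is therefore no closer to a treatment effect in any useful sense.

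**The case for a change.** The strongest reply is that the wording is open, the background speaks of remission as a treatment result, and readers will make the CBTI comparison whether or not it is planned. The possible error runs in one direction and, unlike sampling error, could be removed with data already collected: count the patients who started at 7 or below and show a second rate without them. Under the step 4 assumptions the chance that at least one of 40 started there is 73% or more.

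The factual premises stand. Nothing in sections 2 and 3 prevents such a patient from being enrolled, and the SAP does not state the denominator. What does not follow is that the tabulation is wrong. The background prose describes earlier CBT-I results and does not define this analysis. A comparison that a reader might make is a matter for careful reporting. The SAP already says that presenting clinical symptoms are described, so starting severity is not hidden, although a count at 7 or below is not promised. The extra restricted rate would be one more post hoc choice on smaller groups.

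**Conclusion.** The concern does not hold. Read as its wording suggests, the SAP reports who is in remission at posttreatment and at follow-up, by arousal group, and the all-patient rate is the right quantity for that. The conclusion rests on that reading and on the absence of any planned comparison with CBTI remission rates; it does not depend on the effect being small. The effect is zero if no patient started at 7 or below, 0.8-6.6 points (0.26-0.91 standard errors) under the step 4 assumptions, and larger only if many patients started low and stayed there. The documents do not show that any such patient was enrolled. The analysis is labelled post hoc, and the Aim 1 and Aim 2 paired t-tests are untouched. What remains is an unstated denominator in an exploratory table, which is missing detail and not a flaw in the analysis.

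### The exploratory comparison of remission by high versus low cognitive arousal discards information from a continuous score and, on its likeliest reading, shows co-occurrence only

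*Combined protocol and SAP*

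**What the plan says.** The Statistical Analysis Plan sets out paired t-tests as the main analyses, "with a significance value of .05". It then adds exploratory work: "In addition, we conducted posthoc analyses to further" explore the data. One of these analyses compares rates of insomnia remission "and major depression among patients with high vs low cognitive arousal at posttreatment and follow-up".

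Four things are not stated for this comparison:

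- **Scale.** The assessment list in protocol section 3 (Study Procedures) labels the PSAS, PSWQ and RRS Brood as arousal measures, and adds the PTQ for repetitive negative thinking.
- **Cut-off** between high and low, and its source.
- **Visit** that supplies the arousal score. The closing time phrase can attach to the groups, to the rates, or to both.
- **Test**, if there is one.

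The remission threshold is not restated in the SAP either. Protocol section 2 treats ISI above 7 as non-remission at entry, which implies remission at 7 or below.

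Protocol section 1 gives the rationale: the group's earlier research "suggests that inadequate CBTI response is linked to residual symptoms of cognitive-emotional arousal (i.e., rumination, worry"). The end of that section adds that improvement may be due to reduced arousal and that the findings could help clinicians triage patients.

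**The concern.** Of the analyses in the SAP, this is the only one that relates arousal to remission. The Aim 2 t-test shows whether arousal falls, not whether lower arousal goes with recovery. Readers interested in the mechanism will therefore turn to this table, although it is exploratory.

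Two weaknesses follow from its form. Reducing a score to two groups treats patients just either side of the cut as different and patients far apart on the same side as alike, which wastes information in a small sample. And if both measures come from the same visit, better sleep may have lowered arousal as easily as the reverse. The unstated scale and cut-off add a reporting gap: a reader cannot tell whether they were fixed before the data were seen.

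**Working it through.** **1. The plan's own figure.** Protocol section 3 states, "for a two-tailed test with alpha = .05, a N = 34 sample size will have a .81 power", with d = .50. Exact noncentral-t power with df = 33 and noncentrality .50 × √34 = 2.915 is .808, so the .81 reproduces. At N = 40 it is .869. These figures concern the paired t-test; the documents give none for the arousal comparison.

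**2. Inputs for the arousal comparison.** n = 34 and n = 40 and the two-sided .05 level come from the documents. The documents give no remission rate or correlation, so these are assumed: 50% remission, with arousal and a latent outcome bivariate normal with correlation r.

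**3. What a median split sees.** With both variables cut at the median, the remission rate is 1/2 + arcsin(r)/π in the low-arousal group and 1/2 − arcsin(r)/π in the high-arousal group.

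- r = .3: .5 ± .3047/3.1416 = 59.7% versus 40.3%
- r = .5: .5 ± .5236/3.1416 = 66.7% versus 33.3%

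Simulated power at n = 34-40:

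| Analysis | r = .3 | r = .5 |
|---|---|---|
| Median split, chi-square | about 21% | 51-53% |
| Median split, Fisher | 12-13% | 37-41% |
| Continuous score, two-sample t-test | 27-33% | 68-77% |

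**4. False positives when arousal and remission are unrelated** (simulated at n = 34 and 40; 30% or 50% remission, except the third row, which is 50% only):

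| How the cut is set | Chi-square | Fisher |
|---|---|---|
| One scale, median fixed beforehand | about 5-6% | 2.0-2.6% |
| One scale, best of three cuts | 11-12% | 6-9% |
| One scale, best cut from 20th to 80th percentile | about 29% | not run |
| One scale, best cut in the middle half | about 26% | 16-17% |
| Best cut in the middle half over four scales (correlation .6 assumed) | 62-63% | 44-46% |

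Separately, two outcomes at two visits make four tests. If independent and unadjusted, the chance of at least one false positive is 1 − .95⁴ = 18.5%.

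**5. Time order.** Suppose arousal has no effect on later ISI, the same-visit correlation of arousal with ISI is .4 to .6, ISI correlates .3 to .5 over time, and half the patients remit.

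- Same-visit remission, low versus high arousal, is about 63% versus 37% (correlation .4) to 70% versus 30% (.6). A large gap appears with no forward effect.
- Moving the arousal score to the earlier visit is not enough. The lagged correlation is the product of the two, .4 × .3 = .12 to .6 × .5 = .30. The formula in step 3 then gives 53.8% versus 46.2% up to 59.7% versus 40.3%.
- An unadjusted test of posttreatment arousal against 6-month remission is falsely significant in 8-9% of simulated trials (.4, .3), 20-23% (.5, .5) and 28-32% (.6, .5). Adjusting for posttreatment ISI returns this to about 5-6%.

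**6. The pretreatment median as a fixed cut.** If arousal falls by .5 to 1.0 SD, the share still above the old median is Φ(−.5) = 31% to Φ(−1.0) = 16%. Simulated power at r = .5 is then 30-45% (n = 34) and 38-52% (n = 40), no better than a posttreatment median split and often worse.

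**The case against.** The SAP calls this analysis post hoc and claims no time order for it. The aims are pre-to-post changes tested by paired t-tests, and describing rates by group is legitimate in a single-arm pilot. The rationale in protocol section 1 speaks of a link, not of arousal driving non-response, and the remark that improvement may be due to lower arousal is attached to the Aim 1 and 2 findings rather than to this table. All of that stands, and it keeps the point at the level of an exploratory analysis.

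Three stronger readings are tempting, and the documents do not support them.

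- **That splitting the score itself creates a chance link.** It does not: a cut fixed beforehand holds about 5-6% with chi-square and less with Fisher.
- **That the cut-off was searched for.** An unreported cut-off is not evidence of a searched one. The figure of about 29% needs a full search and an uncorrected chi-square; three candidate cuts give 6-12%, depending on the test.
- **That arousal and remission are known to be measured at the same visit.** This is the likeliest reading, but the wording leaves it open.

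The power gap also depends on an assumed correlation. At r = .3 it is smaller in absolute terms, and neither method has good power.

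**Conclusion.** The concern holds as a cheap improvement to an exploratory analysis. The split gives up roughly 15 to 25 percentage points of power at r = .5 against chi-square (51-53% versus 68-77%), and more against Fisher. This loss applies even if the cut-off was fixed properly in advance. The figures rest on assumed 50% remission, a latent-normal model and n = 34-40; complete-case numbers at 6 months could be lower. They are for remission only. The same loss of information affects the major depression comparison, but its size was not computed.

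On the same-visit reading, the table shows that low arousal and remission occur together and cannot show which came first. A reader might infer from it that residual arousal causes poor outcome; the SAP does not say so, and the table could not establish it. Inflated false positives are a possibility that the documents neither show nor exclude. The primary paired t-tests are unaffected.

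**What to change.** 1. **Name one arousal scale** for this analysis. Fixing a cut-off without naming the scale leaves the larger source of inflation open.
2. **Analyse the score as continuous:** either the mean difference in arousal between remitters and non-remitters, or one logistic slope, with a 95% interval. State the remission threshold and the visit of each measure.
3. **For time order,** relate posttreatment arousal to 6-month ISI, adjusting for posttreatment ISI. The adjustment is essential, for the reason shown in step 5 of the working.
4. **If a high/low table is kept for display,** state its cut-off, the source of the cut-off and the visit, and label a same-visit table as descriptive co-occurrence. Do not use the pretreatment median as the cut.

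The cost is SAP wording and one re-run on data from the three assessments already scheduled. The drawback is that a slope or mean difference is slightly less simple to present than two percentages, and the analysis remains exploratory.
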